3.5.3.2 Incident rates calculation for Active Treatment Period

Incidence rates of AEs which adjust for patient-years on study will be summarized for the Active Treatment Period as indicated previously. The total time on study (patient-years) will be calculated as described in Section 3.5.2. Incidence per 100 patient-years on study will be presented, defined as: [Number of subjects reporting at least one AE during the period / Total time on study (patient-years)] \times 100.

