3.2.1 Analysis Periods

There are four periods which will be used for analysis and are defined as:

- MAD Period: Analyses include data from MAD, Part 1.
- LTE Period: Analyses include data from LTE, Part 2.
- MAD+LTE Period: Analyses include integrated data from both MAD, Part 1 and LTE, Part 2, regardless of a subject's randomization assignment or LTE enrollment status. For example, a subject receiving MAD placebo treatment who does not enroll in LTE will still contribute data from the MAD to this analysis.
- Active Treatment Period: Analyses include data from study periods in which a subject receives active ISIS 814907 treatment. (Note: Study periods refer to Part 1 and/or Part 2, including post-treatment follow-up but excluding any variable gaps in time between Part 1 and Part 2 for subjects in Cohorts A and B). Data collected during a placebo dosing period are not included (except relevant baseline data). Subjects who receive MAD active treatment will contribute data regardless of LTE enrollment status. Subjects who receive MAD placebo treatment will only contribute data if enrolled and dosed in the LTE.

In general, listings will be created for the MAD Period and the MAD+LTE Period.

Safety, pharmacodynamic and exploratory analyses will be conducted for the MAD Period and the LTE Period separately.

The MAD+LTE Period will be used to analyze select biomarkers, neuroimaging and key clinical assessments:

- o MRI (exploratory)
- o Tau-PET/FDG-PET
- o CSF biomarkers including but not limited to total tau, phospho-tau and A-beta42
- o MMSE
- o RBANS
- o CDR

The Active Treatment Period will be used to analyze select safety endpoints including:

- Laboratory assessments: Potential clinically significant laboratory abnormalities, hepatotoxicity, and shift analyses
- o CSF Safety Panel
- o Safety MRIs
- o Incidence rates for treatment emergent adverse events (TEAEs) and serious TEAEs

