3.5.2 Time on Study Analysis

The time on study analysis described below will be included in the final analysis only.

Time on study (years) will be summarized by analysis group for the MAD, LTE, MAD+LTE and Active Treatment Periods using descriptive statistics. Total time on study (patient-years) in each analysis group will be included in the summaries.

Additionally for the MAD+LTE Period, time from last dose date in MAD to first dose date in LTE (years), and time from last study visit date in MAD to first dose in LTE (days and years, separately) will be summarized by analysis group using descriptive statistics.

Time on study (days) for each subject is defined as:

- MAD Period, LTE Period separately: last study visit date within the Period first dose date within the Period + 1
- Active Treatment Period, early starters: (last study visit date in MAD first dose date in MAD + 1) + (last study visit date in LTE first dose date in LTE + 1). For subjects not enrolled in LTE then it is the same as the MAD Period time on study.
- Active Treatment Period, late starters: last study visit date in LTE first dose date in LTE + 1.
- MAD+LTE Period: (last study visit date in MAD first dose date in MAD + 1) + (last study visit date in LTE first dose date in LTE + 1). For subjects not enrolled in LTE then it is the same as the MAD Period time on study.

Time on study (years) for each subject is calculated as the time on study (days) divided by 365.25. Total time on study (patient-years) is calculated as the sum of time on study (years) across subjects within the analysis group and period.

For the MAD+LTE Period: Time from last dose date in MAD to first dose date in LTE (years) is defined as: (first dose date in LTE – last dose date in MAD + 1)/365.25. Time from last study visit date in MAD to first dose in LTE (days) is defined as: first dose in LTE – last study visit

date in MAD + 1; Time from last study visit date in MAD to first dose in LTE (years) is: (first dose in LTE – last study visit date in MAD + 1)/365.25.

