3.5.3 Adverse Events

3.5.3.1 MAD Period and LTE Period

The incidence (proportion) of treatment-emergent adverse events (TEAEs) will be summarized for the MAD and LTE Periods separately, and incidence (rates) of TEAEs will be summarized for the Active Treatment period where indicated by *. The Medical Dictionary for Regulatory Activities (MedDRA) version 20.0 will be used. Summaries will be presented by preferred term (PT) and system organ class (SOC), unless otherwise indicated, for:

- Any TEAE* (summarized by PT only and by both SOC and PT)
- TEAEs potentially related to Study Drug. Related is defined as "Related", "Possible", or missing relationship to study drug, as determined by the investigator
- TEAEs potentially related to Lumbar Puncture (LP) procedure. Related is defined as "Related", "Possible", or missing relationship to LP procedure
- Any TEAE by severity*. At each level of subject summarization, a subject is classified according to the highest severity if the subject reported one or more events. TEAEs with missing severity will be categorized as "Missing" for this summary
- TEAEs potentially related to Study Drug by severity
- TEAEs potentially related to LP procedure by severity
- Serious TEAEs* (by PT only and by both SOC and PT)
- Serious TEAEs potentially related to Study Drug*
- Serious TEAEs potentially related to LP procedure*
- TEAEs leading to permanent study drug discontinuation* (by PT only and by both SOC and PT)

The number and proportion of LPs leading to TEAEs will be summarized for the MAD and LTE Periods separately. The severity of AEs and SAEs will be graded based on criteria from the Common Terminology Criteria for Adverse Events (CTCAE) Version 4.03, June 2010. SAEs and non-serious AEs that lead to permanent study drug discontinuation will be listed separately. Non-treatment emergent adverse event will be flagged in the data listing.

An adverse event will be regarded as treatment emergent if it is present prior to receiving the first dose of study drug (MAD: ISIS 814907 or placebo; LTE and Active Treatment Periods: ISIS 814907) and subsequently worsened, or is not present prior to receiving the first dose of

study drug (MAD: ISIS 814907 or placebo; LTE and Active Treatment Periods: ISIS 814907) but subsequently appeared.

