If there is no "Formlink" link, and the AE (start date/time) occurs after the subject's first dosing date/time, then the AE is treatment-emergent. Otherwise, if the AE (start date/time) occurs prior to the subject's first dosing date/time, then the AE is not treatment-emergent.

If there is a "Formlink" link between two AE records, then we compare them pairwise, and consider two cases, where we compare the AE severity (mild/moderate/severe) between the two records in the pair. We chronologically order the 2 records (by AE start date) and refer to the "first" and "second" AEs.

Case 1: The first AE record in the pair occurs before first dosing, and the second AE record occurs after first dosing.

If the AE severity or seriousness of the second record is worse than that of the first record, then only the second AE is deemed as TEAE. Otherwise, neither record is considered as TEAE.

Case 2: Both AE records in the pair occur after first dosing.

The worst AE will be deemed as a TEAE.

All TEAEs identified based on the rules above will be summarized in the event number analysis.

The most conservative approach will be used to determine if the event occurs after the treatment. For example, if the onset date or resolution date of an AE is prior to the first study treatment date, it will be considered to have occurred prior to the study period. If the onset or resolution date of an AE is a partial date with only month or year available or completely missing, then the event is assumed to be within the study period unless the year is prior to the year of the first study treatment date, or if in the same year, the month is prior to the month of the first study treatment date.

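### For common adverse events, the Active Treatment Period rate in SAP 3.5.3.2 counts each patient once over time that does not stop at the first event, so it does not properly adjust for patient-years

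*Combined protocol and SAP*

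**What the plan says.** SAP 3.5.3.1 gives proportions for the MAD and LTE Periods separately, and adds that "incidence (rates) of TEAEs will be summarized for the Active Treatment period where indicated by" an asterisk. The marked rows are any TEAE (by preferred term and by system organ class), any TEAE by severity, serious TEAEs (overall, and those related to study drug or to lumbar puncture), and TEAEs leading to permanent discontinuation.

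SAP 3.5.3.2 presents these rates as adjusted for patient-years and defines them as "Number of subjects reporting at least one AE during the period / Total time on study (patient-years", per 100. It takes the denominator from SAP 3.5.2, where "Total time on study (patient-years) is calculated as the sum of time on study (years) across subjects within the analysis group and period". Each patient's time runs from first dose to last study visit: MAD plus LTE for early starters, LTE only for late starters. The Cohort A/B gap is left out (SAP 3.2.1). Nothing ends a patient's time at the event being counted.

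On who contributes, SAP 3.2.1 says: "Subjects who receive MAD placebo treatment will only contribute data if enrolled and dosed in the LTE". SAP 3.2.2.2 and Table B3 list Early Start A, B, C and D, Late Start A+B+C and Late Start D as separate columns. Of event counts the SAP says only: "All TEAEs identified based on the rules above will be summarized in the event number analysis". It defines no events-per-patient-year rate.

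**The concern.** Dividing by patient-years is meant to allow for unequal follow-up. It does so if numerator and denominator match: first events over time until the first event, or all events over all time. Here a patient stops contributing to the numerator at the first event but goes on adding to the denominator. For a rare event this hardly matters. For a common one, the longer the planned follow-up, the lower the figure tends to be, at the same underlying risk.

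Follow-up differs by design between early-start and late-start columns shown side by side, and this is the only rate the SAP defines over cumulative active exposure. A reader could take a lower figure in the longer-exposed patients as a safety finding when it comes from the formula.

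**Working it through.** The SAP states no numeric rate, so there is no figure to reproduce. The formula is applied directly.

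**Inputs from the documents**
- The last MAD visit is Day 253 and the last LTE visit is Day 449 (protocol 3.4.1, 3.4.2). Days are divided by 365.25 (SAP 3.5.2).
- A completing early starter gives (253 + 449)/365.25 = 702/365.25 = 1.922 years. A late starter gives 449/365.25 = 1.229 years. MAD alone is 253/365.25 = 0.693 years.
- Cohorts of 8, 8, 12 and 16 randomized 3:1 give early-start groups of 6, 6, 9 and 12, and late-start groups of 2 + 2 + 3 = 7 (A+B+C) and 4 (D).
- Doses: early start A-C 4 + 5 = 9, early start D 2 + 5 = 7, late start 5.

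**Assumed:** event risk, hazard shape and roll-over. The documents give none of these.

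**Constant hazard h, all completing.** The SAP rate is 100 × (1 - exp(-hT))/T. Expected time at risk is (1 - exp(-hT))/h, so the first-event rate is 100h in both columns.

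| True rate per 100 PY | SAP rate, early | SAP rate, late | Ratio |
|---|---|---|---|
| 10 | 9.1 | 9.4 | 0.97 |
| 20 | 16.6 | 17.7 | 0.94 |
| 50 | 32.1 | 37.4 | 0.86 |
| 100 | 44.4 | 57.6 | 0.77 |
| 200 | 50.9 | 74.4 | 0.68 |
| Everyone has an event | 100/1.922 = 52.0 | 100/1.229 = 81.3 | 0.64 |

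In the last row the figure is fixed by follow-up alone. With the 23-week UK post-treatment period (SAP 1.1), LTE ends at Day 337 + 161 = 498. Follow-up is then 751 and 498 days, and the ratios at 50, 100 and 200 are 0.86, 0.78 and 0.70.

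**Hazard shape (Weibull, 100 × (1 - exp(-cT^k))/T).**
- Declining (k = 0.5, c = 1): 39.0 against 54.5, ratio 0.72.
- Rising (k = 2): ratio 0.80, 1.02 and 1.23 for c = 1, 0.5 and 0.25. The direction can reverse.

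**Roll-over.** If a fraction p of early starters enters the LTE, the early-start rate is 100 × [p(1 - exp(-1.922h)) + (1 - p)(1 - exp(-0.693h))]/[1.922p + 0.693(1 - p)]. At a true rate of 100, the ratio to late start is 0.77, 0.81 and 0.90 for p = 100%, 80% and 50%. It passes 1 when p falls below about 22% to 44%, depending on h. Two early-start columns with 100% and 50% roll-over would read 44.4 and 51.8.

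**Events clustered at dosing (assumed 20% chance per dose).** The SAP rate is 100 × (1 - 0.8^n)/T. The event rate is 100 × 0.2n/T. Expected time at risk, counted up to the dosing day, is 0.603, 0.893 and 0.644 years for Early Start C, Early Start D and late start.

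| Measure per 100 PY | Early C | Early D | Late |
|---|---|---|---|
| SAP formula | 45.0 | 41.1 | 54.7 |
| First events, time at risk | 143.5 | 88.5 | 104.3 |
| All events, total time | 93.7 | 72.8 | 81.3 |

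Risk per dose is equal here, but doses per patient-year are 9/1.922 = 4.68, 7/1.922 = 3.64 and 5/1.229 = 4.07. Neither matched measure brings the columns level, and the SAP formula puts Early Start C below late start when both matched measures put it above. At 5% per dose that order does not change: 19.2 against 18.4 by the SAP formula, 23.4 against 20.3 by events.

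**Precision.** If all 12 Early Start D and all 4 Late Start D patients have an event, the SAP rates are 12/23.06 and 4/4.92 patient-years: 52.0 (exact Poisson 95% interval 26.9 to 90.9) and 81.3 (22.2 to 208.3).

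**The case against.** - **Intent.** A reader might infer that the SAP promises an equal footing between early-start and late-start columns. It does not. It says only that rates allow for patient-years and labels them as time on study; the comparison is inferred from columns set side by side. The early-versus-late comparison planned in the protocol (synopsis, 10.6.4) concerns biomarker and clinical evaluations, and no AE test is planned. This stands.
- **Confounding.** Patients who discontinue Part 1 early cannot enter Part 2 (protocol 6.1.1.3, 8.8.1). Late-start columns therefore hold only Part 1 completers, while early-start columns include patients who stopped. No choice of denominator makes them fully comparable. This stands and belongs in a footnote.
- **The at-risk rate can do worse.** With 20% risk per dose, Early Start C against late start is 143.5/104.3 = 1.38 by time at risk and 45.0/54.7 = 0.82 by the SAP formula, so the first lies further from 1. It reflects real dosing density, but time at risk cannot be offered alone as the fair display. This stands.
- **Other summaries.** LTE proportions compare the groups over the same planned 449 days, patient-years are reported, and an event number analysis is mentioned, though its period is not stated. These are partial cross-checks; none corrects the rate over cumulative active exposure.
- **Importance.** The primary objective concerns ascending doses, and comparisons among early-start columns or pooled dose columns are largely intact because each set shares the same planned follow-up or early/late mix. Small groups may be pooled. This limits the weight of the point.

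None of this makes a once-per-patient count over uncensored time a rate that adjusts for follow-up.

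**Conclusion.** The point holds for common TEAEs in the starred Active Treatment Period rows. Under a constant equal hazard and full completion, the early-start figure is 14% below the late-start figure at a true rate of 50 per 100 patient-years, 23% below at 100, and 36% below if everyone has an event. Conversely, if half the late starters have an event (h = 0.693/1.229 = 0.564), early starters show an equal SAP rate only when 0.5 × 1.922/1.229 = 78% of them do, a hazard of 0.792, about 1.40 times higher. At a true rate of 10 the gap is 3%, so rare serious TEAEs and discontinuations are hardly touched.

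Two stronger readings are tempting and unsupported. One is that longer-exposed patients will always look safer: direction depends on hazard shape and roll-over, and the documents give neither. The other is that the dose-related safety assessment is compromised: those contrasts are largely unaffected unless roll-over differs between columns. The table is descriptive and the groups are small. The change should be made because it is cheap and the rate as written does not do what it is described as doing.

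**What to change.** For the starred Active Treatment Period rows, replace the formula with two measures shown together:

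1. Patients with a first event per 100 patient-years at risk. Time runs from first active dose to the first qualifying event, or to the end of the period if there is none, with the Cohort A/B gap excluded and an exact Poisson 95% interval.
2. All events per 100 total patient-years, with the numbers of patients and events. Give no Poisson interval here, because events within a patient are not independent.

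Show both, because events may cluster around dosing and early-start Cohorts A-C are dosed more densely in Part 1.

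The severity rows classify each patient by worst grade ("At each level of subject summarization, a subject is classified according to the highest severity if the subject reported one or more events"), which does not fit a first-event clock. Keep them as counts and proportions.

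Add a footnote that late-start columns contain only Part 1 completers, that follow-up and dosing density differ, and that early-versus-late AE differences should be read with caution.

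The first measure needs an onset date. The current rule only settles whether an event counts ("partial date with only month or year available or completely missing, then the event is assumed to be within the study period", unless the recorded year or month rules it out), and SAP 3.4.2 otherwise imputes nothing. A simple convention is enough: for example, the earliest date consistent with what was recorded and not before first active dose, with a statement of which linked record's start date is used. This rule only supports the remedy; its absence is not a separate fault in the SAP.

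The cost is SAP wording, that convention and modest programming on data already collected. Common-event rates will read higher and intervals will be wide.

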3.5.4 Prior and Concomitant Medications

Prior and concomitant medications will be coded using WHO Drug dictionary (WHO-DD, Version SEP 2017) and summarized by ATC class, generic name/preferred medical name and by treatment group for the MAD Period and LTE Period separately.

A concomitant medication is defined as medications that were taken on or after the first day of study drug administration within the analysis period. This includes medications that were started prior to the initiation of study drug if their use continued on or after the date of the first dosing. In order to define concomitant medications with missing start or stop dates, the following additional criteria will be used:

- if both the start and stop dates of a particular medication were missing, that medication is considered concomitant;
- if the start date of a medication was missing and the stop date of that medication fell on or after the date of dosing, that medication is considered concomitant;
- if the start date of a medication was prior to the date of first dosing and the stop date of that medication was missing, that medication is considered concomitant; or
- if the start/stop date of a medication is partial then where it is not possible to rule out that it was not taken concomitantly it will be considered concomitant.

Non concomitant medications will be flagged in the data listing.

3.5.5 Columbia Suicide Severity Rating Scale (C-SSRS)

Per study design, the C-SSRS assessments will be scheduled in Part 1 and Part 2.

The C-SSRS collects binary Yes/No responses to 11 categories: five subtypes of suicidal ideation and five subtypes of suicidal behavior, and self-injurious behavior without suicidal intent. Specifically, the following outcomes are C-SSRS categories and have binary (Yes/No) responses. (The categories have been re-ordered from the actual scale to facilitate the definitions of the composite endpoints and to enable clarity in the presentation of the results (Nilsson et. al, 2013).

Suicidal Ideation:

Category 1 – Wish to Be Dead

Category 2 – Non-specific Active Suicidal Thoughts

Category 3 – Active Suicidal Ideation with Any Methods (Not Plan) without Intent to Act

Category 4 – Active Suicidal Ideation with Some Intent to Act, without Specific Plan

Category 5 – Active Suicidal Ideation with Specific Plan and Intent

Suicidal Behavior:

Category 6 – Preparatory Acts or Behavior

Category 7 – Aborted Attempt

Category 8 – Interrupted Attempt

Category 9 – Actual Attempt (non-fatal)

Category 10 – Completed Suicide

Other:

Category 11 – Non-suicidal Self-Injurious Behavior

A numerical score, the Suicidal Ideation Score, will be defined as the highest suicide ideation category (1–5) at which the patient responded "Yes" for the given visit. If the patient did not respond "Yes" to any of these categories, the score will be set to zero. The baseline suicidal ideation score will be summarized as baseline characteristics.

The C-SSRS will be analyzed for the MAD Period and LTE Period separately. For each of the categories above, the number and percent of patients with a "Yes" response at any time post-baseline (regardless of baseline response) will be summarized by treatment group. C-SSRS results will be listed for the MAD and MAD+LTE Periods. All data from patients with a "Yes" response at any time post baseline will be listed separately.

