 - i. In addition to microhemorrhages, the degree of WMH severity will be centrally rated on T2 FLAIR and GRE T2 star images using the Age Related White Matter Changes (ARWMC) scale (e.g., WMHs > 5 mm, rated on a 4-point scale ranging from 0 (no lesions) to 3 (diffuse involvement of the entire region), within 5 regions in each hemisphere; a score of 3 in a region constitutes the presence of diffuse WMH)

- ii. Multiple lacunes are rated as the presence of at least 2 lacunes in the basal ganglia and at least 2 lacunes in the frontal white matter. To meet the criterion for the presence of bilateral thalamic lesions, at least 1 lesion must to be present in each thalamus
- b. Current infectious/metabolic/systemic diseases affecting CNS
- c. History of a serious infectious disease affecting the brain in the 5 years prior to Screening
- d. History of clinically significant head trauma (i.e., any loss of consciousness for > 5 minutes), including motor vehicle accident and/or concussion in the 3 years prior to Screening
- e. MRI scan at Screening shows evidence for a potential alternative etiology for dementia (i.e., non-AD etiology)
- f. History of generalized seizures in the 3 years prior to Screening
- 6. Psychiatric diagnosis/symptoms interfering with assessment of cognition
 - a. Attempted suicide, suicidal ideation with a plan that required hospital admission and/or change in level of care within 6 months prior to Screening. For patients with (i) a suicide ideation score ≥ 4 on the Columbia Suicide Severity Rating Scale (C-SSRS) within the last 6 months, or (ii) suicidal behaviors within the last 6 months (as measured by the answer "Yes" on any of the C-SSRS Suicidal Behavior Items, a risk assessment should be done by an appropriately-qualified mental health professional (e.g., a Psychiatrist or licensed Clinical Psychologist) to assess whether it is safe for the patient to participate in the study. Patients deemed by the Investigator to be at significant risk of suicide should be excluded
 - b. Major depressive episode within 6 months prior to Screening (with the exception of patients in remission on allowed concomitant antidepressant medication) or at risk for psychosis, confusional state or violent behavior in the opinion of the Investigator
 - c. Geriatric Depression Scale Short Form > 6
 - d. History of alcohol or drug dependency/abuse within 3 years prior to Screening

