6.2.2 Columbia Suicide Severity Rating Scale (C-SSRS)

The C-SSRS is a structured tool to assess suicidal ideation and behavior. Four (4) constructs are measured: severity of ideation, intensity of ideation, behavior and lethality of actual suicide attempts. Binary (yes/no) data are collected for 10 categories, and composite endpoints based on the categories are followed over time to monitor patient safety (Posner et al. 2011). It maps to the Columbia-Classification Algorithm for Suicide Assessment (C-CASA) and meets the criteria

listed in the recent FDA draft guidance for assessment of suicidality in clinical trials (FDA Sep 2010). The C-SSRS will be used to assess eligibility for the study and to monitor the patients throughout the study.

A referral for psychiatric evaluation is required for any increase (even if apparently transient) in the suicidal ideation score from baseline to a level that would have been exclusionary for this study. In any event of suspected active suicidal intent or significant suicidal behavior or clinical finding suggesting that the patient is dangerous to himself/herself, the patient should be referred for immediate psychiatric evaluation.

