3.2.3 Baseline definitions

3.2.3.1 MAD baseline

MAD baseline will be used for the MAD and MAD+LTE analysis periods. It is defined as the last non-missing measure prior to the first dose of study drug in the MAD, except in the instances given below:

For vital signs (blood pressure [BP] and heart rate [HR]), baseline will be defined as the
average of the triplicate values collected on Day 1 pre-dose in the MAD. If only one or
two assessments are available, the single assessment or average of the two assessments
will be used.

- o For ECG continuous parameters, baseline will be defined as the average of the triplicate values collected on Day -1 of the MAD. If only one or two assessments are available, the single assessment or average of the two assessments will be used. For ECG interpretation, baseline will be defined as the worst categorical results of the triplicate results collected on Day -1 of the MAD.
- For PD biomarkers, baseline will be defined as the average of the Screening and Day 1 pre-dose values in the MAD.
- o For C-SSRS suicidal ideation score, baseline will be defined as the maximum score collected on Day -1 and Day 1 pre-dose in the MAD.

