3.2.3.2 Active treatment period baseline

Active treatment period baseline will be used to analyze the LTE Period and the Active Treatment Period. Active treatment period baseline is the same as the MAD baseline for early start subjects, and for late start subjects is the last non-missing measure collected prior to the first dose of study drug in the LTE except in the instances below:

- o For vital signs (blood pressure [BP] and heart rate [HR]), as the average of the triplicate values collected on Day 1 pre-dose in the LTE. If only one or two assessments are available, the single assessment or average of the two assessments will be used.
- For ECG continuous parameters, as the average of the triplicate values collected immediately prior to first dose in the LTE. For ECG interpretation, baseline will be defined as the worst categorical results of the triplicate results collected immediately prior to first dose in the LTE.
- For C-SSRS suicidal ideation score, as the maximum score collected on Day -1 and Day 1 pre-dose in the LTE.

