3.4.4 Demographic and Baseline Characteristics

Demographic and Baseline characteristics will be summarized using descriptive statistics by analysis group based on the ITT population for the MAD, LTE and Active Treatment Periods separately.

Demographics include age, gender, ethnicity, race, education level in ISCED, weight, height, BMI. Height was measured at MAD Screening only, at other visits other than Screening, BMI (kg/m²) could be computed using the formula:

BMI = (weight in kilograms) / [height in cm / 100]².

Baseline characteristics include individual patient CSF volume (spinal CSF volume, cranial CSF volume, and total CSF volume) and brain volumes (whole brain, ventricular, left and right hippocampal volumes), ARWMC total score; C-SSRS suicidal ideation score and clinical assessment scales (RBANS, MMSE, FAQ, NPI-Q, MHIS, CDR global and memory score, CDR Sum of Boxes, GDS-SF); CSF AD biomarkers (total tau, phospho-tau, A-beta42), CSF NfL & total NfH; prior and concomitant anti-dementia medication (cholinesterase inhibitors and memantine), estrogen replacement therapy, low dose antipsychotic medication, aspirin, fish-oil; and genetic profile (APOE, CD33, BCHE, H1 MAPT haplotype).

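### The only group-level post-baseline C-SSRS table ignores baseline, so no planned summary by group separates new or worsened suicidal ideation from ideation already present

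*Combined protocol and SAP*

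**What the plan says.** SAP 3.5.5 defines the Suicidal Ideation Score at a visit as the highest ideation category (1 to 5) answered Yes, or zero if none. The C-SSRS is analysed for the MAD and LTE Periods separately. For each of 11 categories, the number and percentage of patients with any post-baseline Yes are tabulated; the rule reads "regardless of baseline response) will be summarized by treatment group". Results are listed for the MAD and MAD+LTE Periods, with a separate listing of all data for patients with a post-baseline Yes.

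The baseline is defined in SAP 3.2.3:

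- MAD (3.2.3.1): the higher of the ideation scores recorded on Day -1 and before dosing on Day 1.
- LTE and Active Treatment Periods, late starters (3.2.3.2): "For C-SSRS suicidal ideation score, as the maximum score collected on Day -1 and Day 1 pre-dose in the LTE".
- The same periods, early starters (3.2.3.2): "Active treatment period baseline is the same as the MAD baseline for early start subjects".

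Its stated use is descriptive. SAP 3.5.5 says: "The baseline suicidal ideation score will be summarized as baseline characteristics". SAP 3.4.4 includes "C-SSRS suicidal ideation score and clinical assessment scales" among the baseline characteristics.

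Protocol 6.2.2 makes psychiatric referral mandatory when there is "any increase (even if apparently transient) in the suicidal ideation score from baseline to a level that would have been exclusionary for this study". Exclusion 6a in protocol 5.1.2 makes an ideation score of 4 or more in the last 6 months a reason for a risk assessment, and then says: "Patients deemed by the Investigator to be at significant risk of suicide should be excluded".

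**The concern.** The C-SSRS is a listed safety endpoint in a study whose primary objective is safety and tolerability. The question a reader brings to the table is whether ideation or behaviour appeared or worsened on drug more often than on placebo. A count that ignores baseline does not answer that.

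Patients with ideation can enter. Scores of 1 to 3 carry no C-SSRS restriction in 5.1.2, and a score of 4 or more is not exclusionary in itself. The Part 2 criteria for Cohorts A and B contain no C-SSRS criterion, and Cohorts C and D are not reassessed before Part 2. A late starter whose ideation began on placebo in Part 1 and continued would be counted in the LTE table under active drug. The LTE baseline of 3.2.3.2 would identify that patient, but the table does not use it.

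**Working it through.** **1. How the SAP treats baseline in its other safety summaries**

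| SAP section | Summary | Use of baseline |
|---|---|---|
| 3.5.3 | TEAEs | Absent before first dose, or present and worsened |
| 3.5.6 | Laboratory shifts | From baseline to post-baseline minimum and maximum |
| 3.5.6.1 | Potentially clinically significant laboratory values | Patients already abnormal at baseline are left out |
| 3.5.10 | Safety MRI abnormalities | New or worsening |
| 3.5.5 | C-SSRS | None |

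C-SSRS is the exception among these. SAP 3.5.5 specifies no shift, change, new-onset or worsening summary. It mentions composite endpoints when explaining the category order but defines none.

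**2. Weight of one patient.** The plan states no C-SSRS rate, so there is no figure of its own to reproduce. Group sizes follow from the cohort sizes (8, 8, 12, 16) and the allocation in protocol 3.1.1 and SAP 1.1: a 1:1 sentinel pair, then 5:1, 8:2 or 11:3.

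- Active: 1+5 = 6, 1+5 = 6, 1+8 = 9, 1+11 = 12 (total 33).
- Placebo: 2+2+3+4 = 11. Check: 33 + 11 = 44, the planned number.

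One patient weighs 100/n: 100/6 = 16.7 points (10 mg and 30 mg), 100/9 = 11.1 (60 mg), 100/12 = 8.3 (115 mg) and 100/11 = 9.1 (pooled placebo).

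Example: in one category row, one placebo patient with long-standing ideation (1/11 = 9.1%) and one new case at 115 mg (1/12 = 8.3%) look alike. Counting new cases only, the row would read 0/11 against 1/12.

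**3. Chance that a group contains such a patient.** The documents give no baseline prevalence, so p is assumed. The chance of at least one baseline-positive patient is 1 − (1 − p)^n:

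| p | n = 6 | n = 9 | n = 12 | n = 11 (placebo) |
|---|---|---|---|---|
| 2% | 11% | 17% | 22% | 20% |
| 5% | 27% | 37% | 46% | 43% |
| 10% | 47% | 61% | 72% | 69% |

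**4. Share of counted patients who are not emergent.** Here p is baseline ideation that persists without worsening, and e = 5% is new onset in the rest (both assumed). Share = p / [p + (1 − p)e]:

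- p = 2%: 0.02 / (0.02 + 0.98 × 0.05) = 0.02 / 0.069 = 29%
- p = 5%: 0.05 / (0.05 + 0.95 × 0.05) = 0.05 / 0.0975 = 51%
- p = 10%: 0.10 / (0.10 + 0.90 × 0.05) = 0.10 / 0.145 = 69%

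**5. Protocol 6.2.2 against 5.1.2.** The referral trigger needs an ideation score level that would have excluded the patient. Exclusion 6a names a score (4 or more), but as a prompt for a risk assessment; exclusion then depends on Investigator judgement. The level on which 6.2.2 relies is not set in 5.1.2.

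**The case against.** The case for leaving the plan as it is has weight.

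- **Labelling and compliance.** The table says openly that it ignores baseline. It is descriptive, with no test. Protocol 10.6.2 asks only that C-SSRS be summarised by treatment group, so the SAP complies.
- **Resolution by category.** A patient who moves from category 1 to category 4 adds a count in the category 4 row, and behaviours have their own rows. Baseline ideation that resolves before the first post-baseline assessment is not counted.
- **Listings.** With about 44 patients, the separate listing of post-baseline positives lets a reader compare each patient with baseline, alongside the baseline summary of SAP 3.4.4.
- **Exclusions.** Exclusion 6 also removes recent attempts, recent ideation with a plan that led to admission or a change in level of care, recent major depression unless in remission on allowed medication, and GDS-SF above 6. Prevalence may be at the low end of the range.

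All of this stands, and it limits the point. It does not supply a comparison by group of new or worsened ideation against placebo; a reader would have to build that by hand.

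Three stronger readings are not supported. A reader might infer that the C-SSRS baseline is never used, but SAP 3.4.4 and 3.5.5 use it descriptively. A reader might infer that the table presents pre-existing ideation as treatment-emergent, but it makes no such claim. A reader might take 6.2.2 as the protocol's definition of the analysis signal, but it is a trigger for individual care.

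**Conclusion.** The point holds as a gap in the planned summaries. Persisting and emergent ideation are pooled in the only group-level post-baseline table, and the baseline that would separate them is already defined.

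The weight of one patient, 8.3 to 16.7 points, follows from the planned group sizes. The 29% to 69% range is illustrative: it rests on assumed prevalence, on full persistence without worsening, and on 5% new onset. It should not be read as saying that most counted patients would be non-emergent; at 2% prevalence most would be emergent.

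The mismatch between protocol 6.2.2 and exclusion 6a is separate and holds whatever is decided about the table. A reader might infer that referral has no working trigger at all. That goes too far, because 6.2.2 separately requires immediate referral for suspected active suicidal intent, significant suicidal behaviour or a finding that the patient is a danger to himself or herself.

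**What to change.** Keep the existing table in SAP 3.5.5. Add, by analysis group for the MAD and LTE Periods:

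1. the number and percentage of patients whose maximum post-baseline ideation score exceeds the baseline of SAP 3.2.3, with new scores of 4 or 5 shown separately;
2. the number and percentage with new suicidal behaviour. SAP 3.2.3 gives a special C-SSRS baseline for the ideation score only, so behaviour would use the general last-non-missing rule; 3.5.5 should say so.

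For early starters the LTE comparison uses the MAD baseline, so ideation that arose in the MAD and continued would count as emergent again in the LTE. Flag events that began in the MAD.

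Separately, reconcile the referral trigger in protocol 6.2.2 with exclusion 6a in 5.1.2. Which level applies is a clinical decision for the sponsor.

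The cost is one additional table from data already collected, one sentence on the behaviour baseline, one flag and one protocol clarification.
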